The primary efficacy analyses will be conducted using the modified intention to treat (mITT) population. The primary analysis is a Cox proportional hazards model with treatment assignment as a fixed covariate with a proportional effect. A one-sided p-value for the test of a hazards ratio of 1 compared to the alternative of a hazard ratio greater than 1 (upamostat reduces time to resolution of symptoms) will be presented and used for testing superiority. An interim analysis will be conducted when 50% of maximum enrollment has reached 28 days of exposure. A Kim-Demets (with parameter 2) spending function will be utilized for testing for superiority of upamostat at the interim and final analysis. At the interim analysis, futility analyses will be conducted, where enrollment to the upamostat cohort will be stopped if the predictive probability of superiority by the final sample size is less than 5%.

The hazard ratio for the time to resolution of COVID-19 will be presented with 95% confidence intervals. Additional sensitivity analyses for the primary analysis will utilize additional covariate adjustments in the Cox proportional hazards model.

C 13.5.1.2 Secondary Outcome: Clinical

For each analysis, a 5% two-sided significance will be used. 95% confidence intervals will be presented to summarize each effect estimate. Dichotomous outcomes will be summarized with relative proportions. Ordinal outcomes will be summarized with stacked bar plots, cumulative proportion graphs, and percentiles. Kaplan-Meier plots will be used for summarizing time to event outcomes. Continuous measures will be summarized box plots (means, medians, and inter-quartile ranges).

Each of the secondary analyses will be conducted using the modified intention to treat (mITT) population. Each analysis will be repeated using the per protocol population.

- Change in overall COVID-19 symptom severity score from Day 0 through Day 28

The overall symptom severity question on the Daily Symptom Follow Up Questionnaire will be used for this secondary endpoint. A mixed model repeated measure (MMRM) model will be

used to model the symptom severity score at each day using the baseline symptom score, participant, day, and treatment by day as covariates. The treatment effect by day will be summarized.

- Proportion of participants in each treatment group developing new COVID-19 symptoms rated as severe from Day 0 to Day 28

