An interim analysis will be conducted when 50% (n=150) of participants have reached Day 28 of study. There are prospectively defined criteria for determining superiority of upamostat to its control arm or determining futility on upamostat to its control arm. The DSMB will evaluate safety and need to stop for safety concerns. The detailed rules for declaring superiority/futility are described in C 13.9 Sample Size Determination. Table 2 highlights the interim analysis plans for upamostat.

Table 2 Analysis Schedule and Actions Reviewed at Interim Analysis

Analysis Point	Test for Superiority	Futility Analysis	Safety Analysis
75 randomized to upamostat completing Day 28 post enrollment	Cox Proportional hazards analysis for superiority on the primary outcome; Kim-Demets alpha-spending adjustment	Futility triggered if predictive probability of superiority is less than 5%	DSMB review of safety for continued randomization
150 randomized to upamostat completing Day 28 post enrollment	Final analysis of superiority; Adjusted final nominal alpha		

The interim analyses will be conducted by an unblinded and firewalled external DSMB. The DSMB will provide any recommendations based on the interim efficacy analysis triggers and additionally will review and make recommendations on safety at each interim analysis.

The nominal alpha at the interim analysis will be calculated based on the exact sample size for the interim analysis using the Kim-Demets spending function. As an example, if there are exactly 75 patients on the upamostat arm at the interim analysis then the nominal one-sided alpha at the interim would be 0.00625 with a final analysis nominal alpha of 0.02178.

C 13.7 Final Analysis Plan

Statistical analysis of this PSA will be the responsibility of the IND Sponsor. A statistical analysis plan (SAP) will be finalized prior to the interim analysis and will provide a detailed description of the statistical analyses described in this section.

C 13.9 Sample Size Determination

The maximum sample size for the upamostat arm primary analysis is 300 participants with 1:1 allocation to the upamostat arm and its control arm. The maximum sample size of 300 participants (150 active and 150 controls) and the adaptive design provides 90% power to detect a hazard ratio of 1.50 (a 33% reduction in median time to resolution) and approximately 80% power for a hazard ratio of 1.42 (a 30% reduction in the median time to resolution).

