4.10. Derivations, Data Handling Conventions and Missing Data

Baseline will be defined as the last assessment prior to the first dose date/time (or randomization if patient was not treated).

Study Day will be derived as (assessment date – date of first dose) + 1.

Event durations in days will be derived as (end date – start date) + 1.

Missing data will not be imputed unless otherwise specified elsewhere in this SAP. Missing dates or partially missing dates will be imputed conservatively for adverse events and concomitant medications. Specific rules for the handling of missing or partially missing dates for adverse events and concomitant medications are provided in Appendix A A.

By-visit endpoints will be analyzed using observed data unless otherwise specified. For observed data analyses, missing data will not be imputed, and only the observed records will be included.

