5.2. Efficacy Assessments

The key efficacy assessment in the early treatment indication is time to sustained alleviation or resolution of symptoms among patients who were SARS-CoV-2 positive on initial screening at a local laboratory, either by PCR or rapid antigen test. Time to sustained alleviation or resolution of targeted COVID-19 symptoms will be defined as the number of days from randomization in a PSA (Step 2 of randomization) to the first day the participant reports all symptoms as mild or none (≤ 1 on the Daily Follow Up Symptom Questionnaire), or no worse than the usual severity, for at least 3 consecutive days (the first day being considered the Event Day).

Targeted symptoms include stuffy or runny nose, hoarse voice, sore throat, difficulty breathing, cough, fatigue, muscle or body aches, headache, chills or shivering, feeling hot or feverish, nausea, vomiting, diarrhea, loss of taste, loss of smell. The Symptom Severity Score is collected in the Symptom Follow Up Questionnaire as the Overall Symptom Severity. Overall Symptom Severity may be rated none (0), mild (1), moderate (2), or severe (3). Loss of taste and loss of smell may be rated as the same as usual (0), less than usual (1), or no sense of taste/smell (2, considered a “severe” rating).

The general statistical approach will compare outcomes among participants randomized to receive the active agent, upamostat, to outcomes among participants who were eligible to have been randomized to upamostat but who were randomized instead to any of the placebo arms enrolling at that time. This ensures that the comparison is limited to concurrently randomized participants eligible to receive upamostat.

Unless otherwise specified, for each analysis, a 5% two-sided significance will be used. 95% confidence intervals will be presented to summarize each effect estimate. Dichotomous outcomes will be summarized with relative proportions. Ordinal outcomes will be summarized with stacked bar plots, cumulative proportion graphs, and percentiles. Kaplan-Meier plots will be used for summarizing time to event outcomes. Continuous measures will be summarized with box plots (means, medians, and inter-quartile ranges).

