Sustained alleviation or resolution will be defined as the number of days from randomization within a PSA to the first day the participant reports all symptoms as mild or none (≤ 1 or returning to pre-illness levels) for at least 3 consecutive days (the first day being considered the Event Day). Targeted symptoms will be used for analysis (Supplement 3). Symptoms will be collected at Enrollment using the Screening Symptom Questionnaire to establish baseline symptom status.

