5.2.2. Secondary Outcomes: Clinical

- Number and proportion of all cause hospitalizations
 - Timeframe: Day 0 to Day 28
- Number and proportion of all cause deaths
 - Timeframe: Day 0 to Day 28
- Change in overall COVID-19 symptom severity score
 - Timeframe: Day 0 to Day 28
 - A mixed model repeated measure model will be used to model the symptom severity score (Overall Symptom Severity) at each day using the baseline symptom score, participant, day, and treatment by day as covariates. The treatment effect by day will be summarized.
- Number and proportion of participants in each treatment group developing new COVID-19 symptoms rated as severe
 - Timeframe: Day 0 to Day 28
 - A Cox proportional hazards model will be used to analyze development of new severe symptoms. A new severe symptom is defined as scoring from 0 to 1 on any symptom in the questionnaire and subsequently scoring a 3 for that symptom (or a 2 for change in taste or smell). Treatment arm will be modeled with a proportional hazard effect. The hazard ration will be summarized.
- Proportion of participants who report a return to usual state of health
 - Timeframe: Day 7, Day 14, Day 28, Week 8, Week 12
 - A Cox proportional hazards model will be used to analyze the rime to return to usual state of health. Participants without symptomatic COVID-19 will be considered a 0 for return to usual health. Treatment arm will be modeled with a proportional hazard effect. The hazard ration will be summarized.
 - A Kaplan-Meier curve of time to return to usual state of health will be presented.
- Proportion of participants who report a return to usual activities
 - Timeframe: Day 7, Day 14, Day 28, Week 8, Week 12
 - A Cox proportional hazards model will be used to analyze the time to return to usual activities. Participants without symptomatic COVID-19 will be considered a 0 for return to usual activities. Treatment arm will be modeled with a proportional hazard effect. The hazard ratio will be summarized.
 - A Kaplan-Meier curve of time to return to usual activities will be presented.

Analysis population: The mITT population will be used for secondary endpoint analyses. Change in overall COVID-19 symptom severity score will be repeated with the Per Protocol Population and the Baseline COVID-19 PCR Positive Population.

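### The symptom-severity mixed model gives the baseline score one slope for all 28 days; if that slope shrinks as patients recover, the daily treatment effects lose some precision, mainly on Days 1-3

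*SAP*

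**What the plan says.** The endpoint is the change in overall COVID-19 symptom severity from Day 0 to Day 28. Protocol Appendix C, C 13.5.1.2, says a mixed model for repeated measures will be "used to model the symptom severity score at each day using the baseline symptom score, participant, day, and treatment by day as covariates". SAP 5.2.2 repeats the list and names the output: "using the baseline symptom score, participant, day, and treatment by day as covariates. The treatment effect by day will be summarized". Neither lists a baseline-by-day term or a covariance structure, and neither says whether participant is a random or a fixed effect.

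SAP 5.2 gives the scale: "Overall Symptom Severity may be rated none (0), mild (1), moderate (2), or severe (3"). On the source of the outcome it says "The Symptom Severity Score is collected in the Symptom Follow Up Questionnaire as the Overall Symptom Severity". On baseline it says "Symptoms will be collected at Enrollment using the Screening Symptom Questionnaire to establish baseline symptom status".

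Two general rules apply. SAP 5.2: "Unless otherwise specified, for each analysis, a 5% two-sided significance will be used". SAP 4.10: "Missing data will not be imputed unless otherwise specified elsewhere in this SAP". The single imputation in SAP 4.10.1 is headed for resolution of symptoms, so this endpoint appears to rest on observed scores and the model. SAP 5.2.2 repeats the analysis in the Per Protocol and Baseline PCR Positive populations.

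**The concern.** The model lets the treatment effect differ on each day but forces the relation between baseline and outcome to be the same on all of them. In a self-limiting illness this is unlikely to hold. A patient rated severe at entry will probably still score above one rated mild on Day 1, but by Day 28 most scores should be near zero whatever the starting point. A single slope then falls between the early and late slopes. It adjusts too little on the first days and too much at the end, and the unused baseline information stays in the residual.

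The daily treatment effects are the reported result, so the loss falls on what readers will see. Early separation is at least plausible: protocol C 5.4 reports a pilot median of 3 days to resolution of severe symptoms on 400 mg against 8 on placebo. Precision is also likely to be scarcer than planned, because SAP Appendix A records that enrollment ended before the interim trigger.

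**Working it through.** **Figures in the plan.** There is none for this model: no SD, correlation, covariance or power. The stated power concerns the primary Cox analysis (Table 3 gives 0.906 at a hazard ratio of 1.50 and a 9-day control median; a Schoenfeld calculation with 276.7 events and one-sided alpha 0.02178 gives 0.912) and has no bearing here. The one useful input is the 9-day median in C 13.9. If resolution times are exponential, 2^(-28/9) = 0.116, so about 12% of controls are unresolved at Day 28. This supports scores collapsing toward zero.

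**Why the slope should shrink.** The slope on Day t is β_t = ρ_t·s_t/s_x, where ρ_t is the correlation with baseline, s_t the outcome SD and s_x the baseline SD. It falls if the correlation falls, and also if only s_t falls.

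**Formula.** In large samples with complete data and "with 1:1 allocation to the upamostat arm and its control arm", the variance of the Day t treatment effect under a common slope b, divided by that under day-specific slopes, is

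1 + s_x²(β_t − b)² / σ_t², with σ_t² = s_t²(1 − ρ_t²).

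Here b is the generalised-least-squares slope under an unstructured covariance, or the mean slope under a random intercept.

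**Assumed inputs.** s_x = 0.6; s_t = 0.7 on Day 1 and 0.7 or 0.35 on Day 28; ρ_t declining geometrically; residual serial correlation 0.7 or 0.9.

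**Worked cases.**
- *Weak* (ρ from 0.3 to 0.05, constant SD): β_1 = 0.3 × 0.7/0.6 = 0.350, b = 0.173, σ_1² = 0.49 × 0.91 = 0.446. Day 1: 1 + 0.36 × 0.177²/0.446 = 1.025.
- *Strong* (ρ from 0.7 to 0.05, SD halving): β_1 = 0.817, b = 0.210, σ_1² = 0.49 × 0.51 = 0.250. Day 1: 1 + 0.36 × 0.607²/0.250 = 1.53. Day 3 (β_3 = 0.638, σ_3 = 0.544): 1 + 0.36 × 0.428²/0.296 = 1.22.
- *Very strong* (ρ from 0.8 to 0.05, constant SD, random intercept): β_1 = 0.933, b = 0.322, σ_1 = 0.42. Day 1: 1 + 0.36 × 0.611²/0.176 = 1.76. Day 3 (β_3 = 0.760, σ_3 = 0.531): 1.245.
- *SD falls, correlation does not* (ρ = 0.5 throughout, SD halving, serial correlation 0.9): β_1 = 0.583, b = 0.360. Day 1: 1 + 0.36 × 0.223²/0.3675 = 1.05.

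**Ranges over both covariance forms.**

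| ρ, Day 1 to Day 28 | Day 1 | Day 3 |
|---|---|---|
| 0.3 to 0.05 | 1.02-1.06 | 1.01-1.04 |
| 0.5 to 0.05 | 1.08-1.19 | 1.03-1.11 |
| 0.7 to 0.05 | 1.16-1.53 | 1.04-1.22 |
| 0.7 to 0.2 | 1.09-1.36 | 1.04-1.21 |

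In these sets the ratio is at most 1.07 on Day 7 and 1.05 on Day 14, and 1.01-1.19 on Day 28.

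**Against no adjustment.** The unadjusted ratio is 1/(1 − ρ_t²). On Day 1 it is 1.96 at ρ = 0.7 and 1.10 at ρ = 0.3, above the common-slope values in both cases.

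**Simulated 0-3 scores (60 and 150 per arm).** Common slope against day-specific slopes: 1.18-1.35 on Day 1, 1.10-1.14 on Day 3, about 1.00-1.04 on Day 7, 1.05-1.24 on Day 28. The ratios were similar at both sizes. Bias in the treatment effect was at most 0.004 points.

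**The case against.** A main-effect baseline term is a legitimate prespecified choice, and much of the case against pressing this point stands.

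- **The correlations are not in the documents.** A reader might infer that baseline is known to predict the first days strongly and Day 28 hardly at all. Nothing in the plan shows this. Baseline status comes from the Screening Symptom Questionnaire and the outcome from the Follow Up Questionnaire, and neither form is reproduced. If the Day 1 correlation is only 0.3, the loss is trivial: √1.02 to √1.06, or 1-3% on the standard error.
- **The covariance is unstated.** An unstructured 28-day matrix has 28 × 29/2 = 406 parameters, and the plan may intend a random intercept instead. With an equal-variance random intercept the printed variances would be only 1.03-1.09 times larger, spread over all days. The true sampling variance on Day 1 would still be higher (1.2-1.7 in the settings tried), so the loss would remain but the output would not show it.
- **The window is narrow.** Dosing lasts 14 days, and no document says that Days 1-3 carry the expected effect. No key day is named and no decision rests on these estimates.
- **Missing diaries.** A reader might infer that the common slope biases results for participants with gaps. The documents give no rate or pattern of missing diaries, so they do not support that as an expectation. In a deliberately extreme null case (14% missing, dropout of 40% or 5% by baseline and in opposite directions by arm), the common slope produced false effects of -0.05 to -0.07 points on Days 14-28, and day-specific slopes stayed within 0.005. That shows the mechanism is possible, not that it is likely here.

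**Conclusion.** The point holds as a modest loss of efficiency. Both documents cross treatment with day and leave baseline uncrossed. If the baseline slope shrinks over time, the common slope loses precision mainly on Days 1-3 and slightly near Day 28.

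The overall range is about 1.02-1.8 in variance on Day 1 (standard error +1% to +34%, since √1.8 = 1.34) and 1.01-1.26 on Day 3 (up to +12%, since √1.26 = 1.12), with little change from Day 7 to Day 21. This rests on an assumed Day 1 correlation of 0.3 to 0.8. The upper ends need a strong early correlation and should not be read as the expected case.

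The documents do not support reading this as a threat to validity. With complete data, randomisation keeps the treatment effect unbiased. The primary Cox analysis is not affected. Minor priority.

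**What to change.** In SAP 5.2.2, change the fixed effects to baseline score, day, treatment by day, and baseline score by day. Name baseline score by week (four periods) as the prespecified fallback if the model does not converge. The same sentence could state the covariance structure and confirm that participant is random, because with participant as a fixed effect the baseline slope could not be estimated.

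No new data are needed. The cost is up to 27 extra parameters (28 slopes instead of one), or three with the weekly version. That matters somewhat in a trial that ended enrollment before 150 participants had reached Day 28, and it is why the fallback should be written down in advance.

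If unblinding has already occurred, keep the planned model as the reported analysis and add this one as a sensitivity analysis documented in the Clinical Study Report, where SAP section 1 says changes are recorded.

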5.2.3. Secondary Outcomes: Virological

- Comparison of active and placebo treatment groups in time to negative RT-PCR
 - Timeframe: Day 0 to Week 12
 - Time to negative RT-PCR will be defined as the time of the first of two consecutive readings below the lower limit of detection. A Cox proportional hazards model will be used to analyze the time to negative PCR.
 - A Kaplan-Meier curve of time to negative PCR will be presented.

Analysis population: The mITT population will be used for secondary endpoint analyses and will be repeated with the Per Protocol Population and the Baseline COVID-19 PCR Positive Population.

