- Screening Symptom Questionnaire (repeat if visit not performed on same day as Screening)
- Randomization (Step 1)
- Study (IP) Informed Consent (in person)
- Screening assessments (see [Section C 9.2.3 Screening Assessments](#))
- **ECG**
- Eligibility evaluation (review of all screening and eligibility assessments)
- Randomization (Step 2)
- Upper respiratory specimen collection (prior to administration of upamostat or control) (for efficacy assessment)
- Venous blood sampling (prior to administration of upamostat or control)
 - Hematology (prior to administration of upamostat or control)
 - Chemistry (prior to administration of upamostat or control)
 - **Coagulation Studies**
 - **Anti-SARS-CoV-2 IgM and IgG**
 - **Polymorphisms of relevant host cellular proteases**
 - **Whole Blood, Plasma and Serum Storage for Possible Future Research (prior to administration of upamostat or control)**
 - **Pharmacokinetics**
- **Administration of upamostat or control**
- Collect and update contacts
- Dispense study kit
- Adverse event recording and reporting

C9.4.3 Day 3 Visit – ~~Remote~~ or In Person

This visit is scheduled to take place In Person on Day 3. Every effort should be made to complete the Day 3 visit requirements on Day 3; however, the visit may take place — if necessary +/- 1 days.

- ~~SARS-CoV-2 Vaccination Status~~
- Concomitant medication review
- Collect and update contacts
- Daily Symptom Follow Up Questionnaire (daily until day 28 then at **Weeks 8** and 12)
- Upper respiratory specimen collection
- Clinical outcome assessment
- Vital signs
- Physical exam
- Venous blood sampling (for Pharmacokinetics Group A: venous blood sampling should be collected within 2 hours prior to administration of upamostat or control, for Pharmacokinetics Group B: venous blood sampling should be collected 2-4 hours after administration of upamostat or control)
 - Hematology
 - Chemistry
 - **Coagulation studies**
 - **Whole blood, plasma, and serum storage for possible future research**
 - **Pharmacokinetics**
- **ECG**
- Adverse event recording and reporting

C 9.4.4 Day 7 Visit- ~~Remote~~ or In-person

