A Cox proportional hazards model will be used to analyze development of new severe symptoms. A new severe symptom is defined as scoring a 0 to 1 on any symptom in the questionnaire and subsequently scoring a 3 for that symptom (or a 2 for change in taste or smell). Treatment arm will be modeled with a proportional hazard effect. The hazard ratio will be summarized.

- Proportion of participants who report a return to usual state of health at Days 7, 14, 28, Week 8, and Week 12.

A Cox proportional hazards model will be used to analyze the time to return to usual state of health. Participants without symptomatic COVID-19 will be considered a 0 for return to usual state of health. Treatment arm will be modeled with a proportional hazard effect. The hazard ratio will be summarized.

- Proportion of participants who report a return to usual activities at Days 7, 14, 28, Week 8, and Week 12.

A Cox proportional hazards model will be used to analyze the time to return to usual activities. Participants without symptomatic COVID-19 will be considered a 0 for return to usual activities. Treatment arm will be modeled with a proportional hazard effect. The hazard ratio will be summarized.

- Proportion of participants in each treatment group hospitalized for COVID-19, as adjudicated prior to study unblinding.
- Number and proportion of participants hospitalized (all cause) from Day 0 to Day 28
- Number and proportion of participant deaths (all cause) from Day 0 to Day 28

Outcomes will be summarized with relative proportions

C 13.5.1.2 Secondary Outcome: Virological

- Comparison of active and placebo treatment groups in time to negative RT-PCR from Day 0 to Week 12

Time to negative RT-PCR will be defined as the time of the first of two consecutive readings below the lower limit of detection. A Cox proportional hazards model will be used to analyze the time to negative PCR.

C 13.5.1.3 Safety and Tolerability

An external DSMB will conduct interim reviews for safety. Monitoring of unblinded safety data (including AEs, SAEs, and selected laboratory measurements) will occur monthly throughout the study and will be conducted by the DSMB. Only the DSMB is authorized to evaluate unblinded interim efficacy and safety analyses.

Safety analyses will include:

- Incidence of Serious Adverse Events (SAE)

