3.2. Secondary

- To evaluate the clinical efficacy of Investigational Product (IP) compared to control.
 - **Endpoints**
 - a) Number and proportion of all cause hospitalizations
[Timeframe: Day 0 to Day 28]
 - b) Number and proportion of all cause deaths
[Timeframe: Day 0 to Day 28]
- To determine if early treatment with upamostat can reduce disease severity in participants infected with SARS-CoV-2.
 - **Endpoints**
 - a) Change in overall COVID-19 symptom severity score
[Timeframe: Day 0 to Day 28]
 - b) Number and proportion of participants in each treatment group developing new COVID-19 symptoms graded as severe on the symptom scale
[Timeframe: Day 0 to Day 28]
 - c) Number and proportion of participants who report return to usual state of health

[Timeframe: Days 7, 14, 28, Week 8, Week 12]

d) Number and proportion of participants who report return to usual activities

[Timeframe: Days 7, 14, 28, Week 8, Week 12]

- To determine if early treatment with upamostat can decrease the incidence of hospitalization due to COVID-19.
 - **Endpoint:** Number and proportion of participants hospitalized for COVID-19 [Timeframe: Day 0 to Week 12]
- To evaluate virologic efficacy of upamostat compared to placebo.
 - **Endpoint:** Time to negative PCR [Timeframe: Day 0 to Week 12]

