4.10.2. Time to Negative PCR

Negative PCR is defined as a quantitative PCR result below the lower limit of detection.

Time to negative polymerase chain reaction (PCR) will be defined as the number of days from baseline positive PCR (Day 0) to the first of 2 consecutive negative PCR results.

- If only the final collected PCR is negative, this will be the date of negative PCR.
- If the final collected result is positive, the participant will be assumed censored without negative PCR

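### The only virologic endpoint is analysed without Day 0 viral load; if that load predicts clearance, power is lost, by an amount the documents cannot fix

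*SAP*

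**What the plan says.** SAP 3.2 sets the objective "To evaluate virologic efficacy of upamostat compared to placebo" and gives it a single endpoint, time to negative PCR. SAP 4.10.2 states: "Negative PCR is defined as a quantitative PCR result below the lower limit of detection". It counts time as "the number of days from baseline positive PCR (Day 0) to the first of 2 consecutive negative PCR results". Protocol C 13.5.1.2 agrees: "Time to negative RT-PCR will be defined as the time of the first of two consecutive readings below the lower limit of detection".

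The model is in SAP 5.2.3: "A Cox proportional hazards model will be used to analyze the time to negative PCR", with "Timeframe: Day 0 to Week 12". No covariate is named there or in the protocol. SAP 5.2.3 adds a Kaplan-Meier curve and repeats the analysis in the Per Protocol and Baseline COVID-19 PCR Positive populations. SAP 5.2.5 adds subgroups by age, sex, vaccination and country. None of these uses the measured load; the baseline PCR enters only as positive or negative (SAP 4.9). For testing, SAP 5.2 says that "for each analysis, a 5% two-sided significance will be used".

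The Day 0 material exists. Among the enrollment visit procedures, protocol C 9.4.2 lists "Upper respiratory specimen collection (prior to administration of upamostat or control) (for efficacy assessment".

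**The concern.** A participant who starts with a high load has further to fall before two swabs in a row are below the limit. Differences in starting load between participants can therefore spread clearance times within each arm. An unadjusted Cox model leaves that spread unexplained, which pulls the hazard ratio towards 1 and lowers power. It also leaves any chance difference in starting load between arms in the estimate.

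The SAP adjusts for baseline elsewhere: the symptom-severity mixed model includes the baseline score (5.2.2), and the primary outcome has covariate-adjusted sensitivity analyses (5.2.1). The virologic endpoint has neither.

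Efficiency matters more because the trial stopped short. SAP Appendix A says that enrollment ended before the interim trigger, which protocol C 13.6 sets at 150 participants reaching Day 28, half of the planned 300. The final number is not given.

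**Working it through.** **1. The plan's own power figure.** None is given for the virologic endpoint. For the primary endpoint, protocol C 13.9 states 90% power at a hazard ratio of 1.50 with 300 participants (Table 3: 0.906 for a 9-day control median).

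- Exponential times censored at Day 28: the control event probability is 1 − exp(−28·ln2/9) = 0.884, and the active one is 1 − exp(−1.5·28·ln2/9) = 0.961.
- Expected events: 150 × (0.884 + 0.961) = 276.7.
- Fixed-design power: Φ(ln1.5·√(276.7/4) − 1.96) = Φ(1.41) = 0.921.
- With the two-look boundary (interim alpha 0.025 × 0.5² = 0.00625, final 0.02178): 0.915.

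The stated figure is reproduced to within a point.

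**2. Proportional-hazards simulation of the virologic endpoint.** Hazard = (ln2/9)·exp(ln1.5·arm − g·x), where x is standardised Day 0 load and g is the assumed log hazard ratio per SD. The 9-day median and the hazard ratio of 1.5 are borrowed from the primary endpoint. Each event is recorded at the next scheduled swab (Days 3, 7, 10, 14, 28, 56, 84). Two-sided 5%, Efron ties, 1,000 runs per row. The standard error near 50% power is √(0.25/1000) = 1.6 points.

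| g | N=300 power, unadjusted → adjusted | N=148 power, unadjusted → adjusted | N=148 average hazard ratio, unadjusted / adjusted |
|---|---|---|---|
| 0 | 92.7 → 92.7% | 63.2 → 62.4% | 1.46 / 1.47 |
| 0.3 | 86.5 → 90.7% | 58.3 → 62.3% | 1.43 / 1.47 |
| 0.5 | 79.8 → 90.9% | 49.1 → 62.6% | 1.40 / 1.47 |
| 0.8 | 65.2 → 88.9% | 37.8 → 58.3% | 1.32 / 1.45 |
| 1.2 | 50.3 → 88.0% | 28.4 → 55.3% | 1.26 / 1.43 |

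The nominal gain runs from none to 37.7 points (88.0 − 50.3), according to g. No false-positive check was made for this model.

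**3. Viral-decline simulation.** Assumptions, none from the documents: Day 0 load normal with mean 6 log10 and SD 0.75, 1.5 or 2.0; limit 2 log10; linear decline averaging 0.35 log10/day, with log-SD 0.3 or 0.6 between participants; assay SD 0.5; decline 20% faster on drug; baseline-positive only; no dropout. The event follows SAP 4.10.2. 600 runs per row, N=148. R² is between Day 0 load and log clearance time.

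| R² | Day 0 SD / decline log-SD | Power, unadjusted → adjusted | Rejection with no effect, unadjusted / adjusted |
|---|---|---|---|
| 0.06 | 0.75 / 0.6 | 31.5 → 31.5% | 2.5 / 3.0% |
| 0.15 | 0.75 / 0.3 | 64.8 → 72.8% | 2.5 / 3.5% |
| 0.25 | 1.5 / 0.6 | 25.8 → 30.7% | 3.7 / 6.3% |
| 0.35 | 2.0 / 0.6 | 21.7 → 30.7% | 3.7 / 6.5% |
| 0.45 | 1.5 / 0.3 | 44.0 → 67.0% | 2.5 / 3.3% |
| 0.57 | 2.0 / 0.3 | 37.7 → 64.3% | 3.5 / 7.2% |

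At N=300 the gains are 2 to 3 points for R² up to 0.15, 12 to 14 for R² 0.25 to 0.35, and 15 to 26 for R² 0.45 to 0.56.

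**4. Unequal false-positive rates.** The unadjusted test rejects too rarely with no treatment effect. The adjusted test reaches 7.2%; with a standard error of √(0.05·0.95/600) = 0.9 points, that is about 2.5 standard errors above 5%. The nominal gains therefore compare tests of different size.

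**5. Size-matched checks (500 runs per setting).** With 75 per arm, linear decline and each test recalibrated to reject 5% under no effect:

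- Day 0 SD 1.5, log-SD 0.3: the gap fell from 25 points to about 8.
- SD 1.0, log-SD 0.5: the gap was about 3.
- SD 2.0, log-SD 0.3: it stayed near 24.

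If Day 0 instead falls 0 to 3 days before peak load (also an assumption), nominal power at SD 1.0, 1.5 and 2.0 was 58 vs 59%, 46 vs 55% and 38 vs 50%. Size-matched, the gaps were about −1 to +3. A separate set with 70 per arm gave nominal gains of about 6 to 29 points (linear) and 5 to 12 (pre-peak), and about −3 to +16 size-matched. Recalibrated cutoffs from 500 runs are noisy: √(0.05·0.95/500) is about 1 point of size.

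**The case against.** The strongest reply has four parts.

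- **Validity.** An unadjusted Cox test is valid under randomisation, and chance imbalance is not bias. The SAP follows the protocol's endpoint and model for one secondary outcome of a Phase 2 trial. This stands: the point concerns efficiency, not error.
- **Circularity.** A linear decline from Day 0 makes clearance time a function of starting load by construction. Where participants may still be before their peak at Day 0, the gain shrinks or disappears. This stands, and it is why the size can only be given as a range.
- **Unequal size.** Part of the apparent gain is a difference in false-positive rates. This stands too; it reduces the gain, and in some settings removes it.
- **Existing provision.** The repeat in baseline PCR-positive participants deals with some of the baseline virology. It does so only in part, because it separates positive from negative and ignores load among the positives.

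What the reply does not remove is the asymmetry. With no association, adjustment cost essentially nothing (63.2 vs 62.4% at N=148, within simulation error). With a strong one, it usually helped materially.

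**Conclusion.** The point holds conditionally. The only virologic endpoint is analysed with no baseline covariate, although the Day 0 swab is already taken and the endpoint rests on a quantitative result. If Day 0 load is prognostic, that omission costs power. Allowing for unequal test sizes, a fair summary is about none to a few points for a weak association and roughly 10 to 15 points or more for a strong one. Every input on viral load and its kinetics is an assumption, and 140 to 150 participants only illustrates a shortened trial.

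A reader might infer three stronger claims, which the documents do not support:

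- That Day 0 load largely determines clearance time. No passage gives the strength of that link.
- That power is being thrown away at no cost. The nominal gains mix power with test size, and adjustment changes the hazard ratio from a marginal to a conditional effect.
- That the plan is deficient without a model of the viral-load values themselves. Such a model would be an optional addition; the point does not depend on it.

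**What to change.** In SAP 5.2.3, before unblinding, add Day 0 log10 viral load as a covariate in the Cox model for time to negative PCR, and settle in advance:

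- **Scale.** Choose one scale and state it. The documents do not give the reporting unit, and should confirm that the Day 0 swab is run on the same quantitative assay.
- **Day 0 values below the limit.** For example, set to the limit plus an indicator. The rule is needed because SAP 5.2 allows entry on a rapid antigen test, so the mITT population can include PCR-negative participants. For them the clock in SAP 4.10.2, which starts from a positive baseline PCR, is also undefined.
- **Missing Day 0 values.** For example, a missing indicator, so that no mITT participant is dropped.
- **Reporting.** Give the unadjusted hazard ratio alongside, because the adjusted one is a conditional effect and the adjusted test ran somewhat above 5% in some settings.

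Optional supporting work is a Day 0-adjusted analysis of log10 load with values below the limit treated as left-censored. It should note that the Day 7 and Day 10 swabs are self-collected (protocol C 9.4.4 and C 9.4.5).

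The cost is SAP wording and slightly more analysis, with no new samples. Record the change in SAP Appendix A with its timing relative to unblinding. If unblinding has already occurred, report it in the CSR as post hoc.
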